6.4 Interim Analysis

RGD will be considered for early stopping for futility according to the interim analysis schedule and definition specified in the "ALS Master Protocol Recommended Statistical Analysis, Design and Simulation Report" (Appendix 1 to the Master Protocol). RGD will not be stopped early for success.

6.5 Secondary Efficacy Analyses

6.5.1 Hierarchical Testing

Primary inference for secondary efficacy endpoints will be based on analysis of the FAS analysis set or subsets of the FAS analysis set as defined below. Primary estimates and inference for time-to-event endpoints will be by Kaplan-Meier product-limit estimates and log-rank test (see Section 6.5.6 below). Primary estimates and inference for responder endpoints will be by logistic regression as described in Section 6.5.5 with missing data handled as indicated in Section 3.6. Primary estimates and inference for rate of change of continuous endpoints will be by a random-slopes linear mixed model (see Section 6.5.3 below). The sequence for testing secondary efficacy endpoints is the following:

1. Time to first decline of 2 points or greater post-baseline in the ALSFRS-R total score among participants in FAS with bulbar dysfunction at baseline defined as an ALSFRS-R bulbar domain (Q1-Q3) score of less than 12,

2. Proportion of participants experiencing no worsening in the ALSFRS-R bulbar domain (Q1-Q3) score from baseline through Week 24 among all participants in FAS,
3. Rate of change in respiratory function as measured by slow vital capacity (SVC) maximum percent predicted from baseline through Week 24 among participants in FAS with bulbar dysfunction at baseline defined as an ALSFRS-R bulbar domain (Q1-Q3) score of less than 12,
4. Time to first decline post baseline of 1 point or greater in the ALSFRS-R bulbar domain (Q1-Q3) score among all participants in FAS, and
5. Time to death or death equivalent through Week 24 among all participants in FAS.

If the primary analysis indicates a significant slowing in disease progression from the Bayesian shared-parameter, repeated-measures model of ALSFRS-R and mortality, then each secondary efficacy endpoint in succession would be declared significant in the specified sequence using a comparison-wise criterion of two-tailed $p < 0.05$. After the first failure to declare significance, no endpoints lower in the hierarchy can be significant. This sequential closed-testing procedure controls the overall type 1 error rate at 5%. Nominal comparison-wise p-values for secondary efficacy endpoints will also be reported.

All secondary efficacy analyses specified here for hierarchical testing will also be analyzed in the mITT analysis set as sensitivity analyses.

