6.5.3 Random-slopes Model

The specification of the random-slopes linear mixed model and the primary linear contrast for estimating differences in mean rate of progression in a given continuous efficacy endpoint (ALSFRS-R total and domain scores, SVC, HHD upper extremity, lower extremity, and global average percentages, FVC by home spirometry, quantitative voice characteristics, serum creatinine, serum NfL, ALSAQ-40 domain scores and SI, CNS-BFS total score, and CNS-LS score) are revised from those specified in the M-SAP to include a main effect of treatment and main effects of centered baseline Nuedexta use, centered site of symptom onset (bulbar vs. non-bulbar), and their interactions with visit as additional covariates and to specify that study months are calculated as the difference in days from the Baseline Visit to the date of assessment of a given endpoint multiplied by 12 / 365.25.

The model will include fixed terms for month since the Baseline Visit, treatment group, treatment group × month interaction, centered years since ALS symptom onset and centered years since ALS symptom onset × month interaction, centered delta-FRS and centered delta-FRS × month interaction, centered baseline riluzole use and centered baseline riluzole use × month interaction, centered baseline edaravone use and centered baseline edaravone use × month interaction, centered baseline Nuedexta use and centered baseline Nuedexta use × month interaction, and centered site of symptom onset (bulbar vs. non-bulbar) and centered site of symptom onset × month interaction. The following equations describe the model with regimen random effects:

$$\begin{aligned}
 Y_{ij} &= \gamma_1 + a_{k(i)}^0 + b_i^0 + \gamma_2 t_i + \boldsymbol{\gamma}'_3 \mathbf{z}_i \\
 &+ (\gamma_4 + a_{k(i)}^1 + b_i^1 + \gamma_5 t_i + \boldsymbol{\gamma}'_6 \mathbf{z}_i) m_{ij} + \epsilon_{ij} \quad (\text{eqn. 2}) \\
 \{a_k^0, a_k^1\} &\sim N(\mathbf{0}, \boldsymbol{\Sigma}_r), \{b_k^0, b_k^1\} \sim N(\mathbf{0}, \boldsymbol{\Sigma}_p), \epsilon_{ij} \sim N(0, \sigma_\epsilon^2) \\
 \text{Cov}(\mathbf{a}_k, \mathbf{b}_k) &= \mathbf{0}, \text{Cov}(\mathbf{a}_k, \boldsymbol{\epsilon}_{i\cdot}) = \mathbf{0}, \text{and } \text{Cov}(\mathbf{b}_k, \boldsymbol{\epsilon}_{i\cdot}) = \mathbf{0}
 \end{aligned}$$

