6.5.5 Responder Analysis

Analysis of responder endpoints will use logistic regression. The dependent variable will be whether the participant is a responder or not, while the independent variables will be treatment group, baseline ALSFRS-R score, site of onset (any bulbar vs. non-bulbar), riluzole use at baseline, edaravone use at baseline, and delta-FRS. A separate supportive analysis will include centered baseline serum NfL level as an additional covariate.

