6.5.6 Survival and Time to Clinical Events

Survival and time to hospitalizations and clinical events will be analyzed in the FAS, mITT, ECM, ERO, EPP, STF, and SRO analysis sets. Survival analyses that include follow-up beyond the placebo-controlled period will be analyzed in the ERO analysis set. The summaries and analyses of time to death or death equivalent are the same as specified in the M-SAP with the addition of baseline age as a covariate in adjusted models, with the addition that the endpoints of time to death independent of occurrence of death equivalents and time to each of the hospitalization and clinical events will be separately analyzed using the same models, and with an additional adjusted analysis that includes baseline serum NfL level as a covariate. Analysis of time to King's stage 4a or 4b will accommodate interval censoring between ALSFRS-R assessments and will be stratified by baseline King's stage.

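### Low-cost improvement, not an error: key secondary 4 is decided by a log-rank test with no stratum named for baseline bulbar score (12 vs below 12)

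*SAP*

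**What the plan says.** SAP 6.5.1 sets the deciding method for every time-to-event key secondary: "Primary estimates and inference for time-to-event endpoints will be by Kaplan-Meier product-limit estimates and log-rank test", with a pointer to 6.5.6. Key secondary 4 is the time to a first decline of at least 1 point in the ALSFRS-R bulbar domain among all FAS participants.

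SAP 6.5.6 says of the survival analysis: "The summaries and analyses of time to death or death equivalent are the same as specified in the M-SAP". It names no stratum or covariate for key secondary 4. Its one stated stratification concerns time to King's stage 4a or 4b, which "will accommodate interval censoring between ALSFRS-R assessments and will be stratified by baseline" King's stage.

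Key secondary 2 comes earlier in the sequence: "Proportion of participants experiencing no worsening in the ALSFRS-R bulbar domain (Q1-Q3) score from baseline through Week 24 among all participants in FAS". Its logistic model (6.5.5) uses "treatment group, baseline ALSFRS-R score, site of onset (any bulbar vs. non-bulbar), riluzole use at baseline, edaravone use at baseline, and delta-FRS". The section does not say whether the baseline score is the total or the bulbar domain.

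The sequence opens only "If the primary analysis indicates a significant slowing in disease progression", and "After the first failure to declare significance, no endpoints lower in the hierarchy can be significant". Nominal p-values are reported regardless.

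Baseline bulbar score is not a randomization stratum; SAP 2.6 stratifies by riluzole and edaravone use only.

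**The concern.** The SAP itself treats bulbar 12 and below 12 as different populations for this same event. SAP 4.1 lists the endpoint separately for participants below 12, and 4.2 lists it for those at 12. Key secondary 4 pools them. If impaired participants lose a bulbar point sooner, an unstratified log-rank test compares mixed risk sets: the pooled hazard ratio is pulled towards 1, and chance imbalance in bulbar status adds noise.

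The protocol's reason for log-rank tests (section 9.4) is that few events are expected, and it is given for bulbar onset and for death. That fits key secondary 5 and the score-12 part of key secondary 4. It does not obviously fit participants who already have bulbar impairment.

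At stake is some power for key secondary 4 and, through the fixed sequence, access to key secondary 5 (death or death equivalent). The validity of any test is not at stake.

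**Working it through.** **No plan figure to reproduce.** The documents give no event rate, hazard ratio or power for key secondary 4. The design numbers that can be checked agree: 160 at 3:1 gives 120 active and 40 placebo. The number of placebo participants shared from regimens A, B and C is not stated.

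**Why pooling costs power.** Assume 60% of participants are below 12, 45% of score-12 placebo participants have the event by Week 24, and the treatment hazard ratio is 0.70 in both groups. Let k be how many times higher the hazard is below 12.

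- Score-12 placebo cumulative hazard: H = -ln(0.55) = 0.598.
- Event-free share, placebo: P = 0.4·exp(-H) + 0.6·exp(-kH).
- Event-free share, active: A = 0.4·exp(-0.7H) + 0.6·exp(-0.7kH).
- Pooled cumulative-hazard ratio at Week 24: ln A / ln P.

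| k | P | A | ln A / ln P |
|---|---|---|---|
| 1 | 0.550 | 0.658 | 0.70 |
| 2 | 0.402 | 0.523 | 0.71 |
| 3 | 0.320 | 0.434 | 0.73 |
| 4 | 0.275 | 0.376 | 0.76 |

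The pooled effect is barely diluted at k = 2 and visibly diluted at 3 or more.

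**Power of key secondary 4 taken alone.** Simulated under the same inputs (120 active, 12% dropout, visits every 4 weeks, 3,000 trials per cell), unstratified to stratified:

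| k | 160 placebo | 100 placebo |
|---|---|---|
| 1 | 41.7% to 41.8% | 36.9% to 36.0% |
| 2 | 52.4% to 54.4% | 44.1% to 46.6% |
| 3 | 51.4% to 60.5% | 43.1% to 51.0% |

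Type I error at k = 3 with 160 placebo was 4.9% unstratified and 5.2% stratified.

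A wider grid used 40–75% impaired, 100 or 160 placebo, and either hazard ratio 0.70 or slopes multiplied by 0.65, with 5,000 trials per cell. Changes were -0.5 to +1.1 points (1x), +0.1 to +4.9 (2x) and +1.8 to +12.5 (3x), with type I error 4.5–5.4%.

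A separate run used hazard ratio 0.65, 10% dropout, 160 placebo and 15–40% events at score 12, with 4,000 trials per cell. It gave about 0 (1x), 0.0 to +2.8 (2x) and +2.1 to +8.8 (3x). With only 40 placebo the change across 1x to 4x was about -0.3 to +4.

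**Inside the sequence.** Key secondary 4 is formally tested only if the primary and key secondaries 1 to 3 succeed. Under SAP 3.6, death, death equivalent and early termination for progression count as events in one analysis and non-response in the other, so endpoints 2 and 4 count nearly the same outcome. The change in the chance of winning both was simulated with 1,500 trials per cell. Baseline total score was used in the 6.5.5 model, and dropouts' true status replaced imputation:

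- Stratifying endpoint 4 alone: -0.6 to +1.8 points.
- Also adding a 12 vs below-12 term to endpoint 2: -0.9 to +0.3 (1x), +0.4 to +3.0 (2x), +2.2 to +4.9 (3x), +4.8 to +6.3 (3.75x).

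A further check of both changes together gave about -0.6 to +0.1 (1x), +0.6 to +1.9 (2x) and +2.7 to +6 (3x). These joint figures do not include the chance of winning the primary or endpoints 1 and 3.

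**The case against.** The strongest reply is that nothing is broken. The log-rank test is valid, type I error holds, and the sponsor may have preferred a simple test. That stands, and it is why this is an improvement and not a defect.

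Second, the R-SAP lists only departures from the Master SAP, so silence here does not prove that no stratum exists. That also stands. But SAP section 1 ranks the R-SAP above the Master SAP on such matters, so the point can be settled here either way.

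Third, the gain inside the sequence is small. That is true of stratifying endpoint 4 alone, and it is the reason for changing endpoint 2 as well. If the baseline score in 6.5.5 means the bulbar domain, much of the endpoint 2 gain may already be in place. Site of onset in that model may also capture part of it.

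Fourth, the King's stage precedent is an exploratory endpoint outside the hierarchy. It shows that the device is already in the SAP, not that it is required.

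A reader might also infer that key secondary 1 should be decided by an adjusted Cox model. The figures do not support that: with event times grouped by visit, the power change runs from -3.2 to +7.5 points, so it can lose. Nor is it a gap that key secondary 3 has no 12 vs below-12 term. It is restricted to participants below 12, where the term would be constant, and it already adjusts for other covariates ("centered delta-FRS and centered delta-FRS × month interaction, centered baseline riluzole use" among them).

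**Conclusion.** The point holds as an optional efficiency gain. Taken alone, key secondary 4 changes in power by about 0 points if bulbar status is not prognostic, about 0 to +5 at 2x and about +2 to +12 at 3x. The chance of winning endpoints 2 and 4 together, with both changes made, moves by about -1 to +0.3 (1x), +0.4 to +3 (2x) and +2 to +6 (3x or more). Type I error stays near 5%.

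Everything rests on assumed event rates, impaired share, treatment effect and shared-placebo numbers. No regimen effect was simulated, although placebo participants are pooled across regimens. The upper ends need strong prognosis: at 3.75x, for example, a 52% placebo event rate at score 12 implies 1 - 0.48^3.75 = 94% below 12. A reader might infer that the planned test is wrong or that a large gain is assured; the documents support neither.

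**What to change.** Before unblinding:

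1. In SAP 6.5.1, state that key secondary 4 is decided by a log-rank test stratified by baseline bulbar score (12 vs below 12), with the unstratified test as supportive.
2. In 6.5.5, add a 12 vs below-12 indicator to the logistic model for key secondary 2, and say whether the baseline ALSFRS-R score is the total or the bulbar domain.
3. State in 6.5.1 whether any other log-rank test carries strata from the Master SAP. Keep log-rank for key secondaries 1 and 5.

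Blinded pooled event rates by baseline bulbar score would show which part of the range applies.

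The cost is SAP wording and a few lines of code, with no new data. The downside is a loss of up to about 1 point if bulbar status is not prognostic. Any hazard ratio reported alongside the stratified test would be conditional on bulbar status rather than marginal, and should be labelled so.

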6.5.2 Repeated-measures Model

The specification of the repeated-measures linear mixed model and the primary linear contrast for estimating differences in 24-week change from baseline in a given continuous efficacy endpoint (ALSFRS-R total and domain scores, SVC, HHD upper extremity, lower extremity, and global average percentages, FVC by home spirometry, serum creatinine, serum NfL, ALSAQ-40 domain scores and SI, CNS-BFS total score, and CNS-LS score) are revised from those specified in the M-SAP to include a main effect of treatment and main effects of centered baseline Nuedexta use, centered site of symptom onset (bulbar vs. non-bulbar), and their interactions with visit as additional covariates.

The model will include fixed terms for discrete visit, treatment group, treatment group \times visit interaction, centered time since symptom onset and centered time since symptom onset \times visit interaction, centered delta-FRS and centered delta-FRS \times visit interaction, centered baseline riluzole use and centered baseline riluzole \times visit interaction, centered baseline edaravone use and centered baseline edaravone \times visit interaction, centered baseline Nuedexta use and centered baseline Nuedexta use \times visit interaction, and centered site of symptom onset (bulbar vs. non-bulbar) and centered site of symptom onset \times visit interaction. The following equations describe the model with regimen random effects:

$$Y_{ij} = a_{k(i)} + \gamma_1 t_i + \gamma_{2,j} v_j + \boldsymbol{\gamma}'_3 \mathbf{z}_i + \gamma_{4,j} t_i v_j + \boldsymbol{\gamma}'_{5,j} \mathbf{z}_i v_j + \epsilon_{ij} \quad (\text{eqn. 1})$$

$$a_k \sim N(0, \sigma_r^2), \epsilon_{i \cdot} \sim N(\mathbf{0}, \mathbf{R}), \text{Cov}(b_{k(i)}, \epsilon_{ij}) = 0$$

where Y_{ij} is a given efficacy endpoint measured in participant i at visit j , $a_{k(i)}$ is a random intercept for regimen k to which participant i was assigned, v_j is an indicator variable for visit j , \mathbf{z}_i is the vector of covariates (centered time since onset, centered delta-FRS, centered baseline riluzole use, centered baseline edaravone use, centered baseline Nuedexta use, and centered site

of symptom onset) for participant i , t_i is an indicator variable for treatment t to which participant i was assigned, $\gamma_1, \gamma_{2,j}, \gamma_3, \gamma_{4,j}$, and $\gamma_{5,j}$ are estimated parameters and vectors of parameters for the fixed effects, and ϵ_{ij} is the residual for participant i at visit j . The regimen-specific random effects are normally distributed with mean 0 and variance σ_r^2 . The vector of residuals for a given participant are normally distributed with mean $\mathbf{0}$ and an unstructured covariance matrix \mathbf{R} . The regimen-specific random effect for a given participant and residuals for that participant are uncorrelated.

The following SAS code specifies the model:

```
proc mixed data=xxx method=reml;
  class regimen id trtrnd visit;
  model Value = trtrnd|visit
              sx2b1|visit dFRS|visit r1z|visit edv|visit
              NDX|visit bulbar|visit / solution cl;
  random intercept / subject=regimen type=vc;
  repeated visit / subject=id type=un;
```

where `id` is a participant study identifier, `trtrnd` is the randomly assigned treatment group, `visit` is the visit identifier, `Value` is value of the efficacy endpoint being tested for a given participant at a given visit, `sx2b1` is years since ALS symptom onset centered at the sample median, `dFRS` is pre-baseline slope centered at the sample median, `r1z` is an indicator of riluzole use at baseline, `edv` is an indicator of edaravone use at baseline, `NDX` is an indicator of baseline use of Nuedexta centered at the sample median, and `bulbar` is an indicator of bulbar site of onset centered at the sample median. The primary estimate will be the treatment-dependent difference in change from baseline to the Week 24 Visit. The estimate and its 95% Wald confidence bounds will be obtained by a linear contrast of adjusted means. The following SAS code specifies the linear contrast for a regimen with one active treatment assuming an endpoint measured every 8 weeks and that the sort order for treatment group has the active group last and visits are sorted chronologically:

```
estimate "3|Act vs Plb|dWk 24" trtrnd*visit 1 0 0 -1 -1 0 0 1 / cl;
```

A significant difference in 24-week change from baseline in the direction of greater improvement or less worsening among participants randomized to active treatment would support inference of benefit from active treatment for the efficacy endpoint being tested.

The estimand estimated by the primary linear contrast of the repeated-measures linear mixed model is the mean difference in 24-week change from baseline of a given continuous efficacy endpoint in the active treatment group relative to the placebo group in the FAS population. The estimand is defined by the following attributes:

- Treatment: pridopidine administered orally at a dosage of 45 mg BID vs. placebo.
- Population: FAS population as defined in Section 6.1.
- Variables: absolute change in endpoint from baseline to the Week 24 Visit.
- Intercurrent event: treatment discontinuation: handled via treatment policy approach, all data will be used including data collected during the placebo-controlled period after treatment discontinuation. Missing data post-treatment, including data missing due to death, will not be imputed, handled via missing at random assumption.

- Population-level summary: difference in conditional means of active treatment relative to placebo.

Inference from this analysis is supportive of inference from the Bayesian shared-parameter, repeated-measures model for the primary endpoint. A separate supportive analysis will include centered baseline serum NfL level and the interaction of centered baseline serum NfL level and visit as additional covariates.

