9.4 Secondary Efficacy Endpoints

If the primary analysis demonstrates significant slowing of decline in ALSFRS-R among participants randomized to pridopidine, then the following secondary hypotheses will be tested in the specified sequence with overall type I error rate controlled using a sequential closed-testing procedure:

1. Rate of change in ALSFRS-R bulbar subdomain (Q1-Q3) score among participants with bulbar dysfunction at baseline,
2. Rate of change in ALSFRS-R bulbar subdomain (Q1-Q3) score among all randomized participants,
3. Rate of change in the speech sub-score of the ALSFRS-R (Q1) among all randomized participants
4. Rate of change in SVC maximum percent of predicted among all randomized participants,
5. Rate of change in ALSFRS-R bulbar subdomain (Q1-Q3) score among participants with pre-baseline slope ≥ 0.75 points/month,
6. Time to onset of bulbar symptoms among participants free of bulbar dysfunction at baseline,
7. Rate of change in HHD percent change from baseline among all randomized participants,
8. Time to death or death equivalent

Analyses for each secondary hypothesis will use an ITT analysis sample that includes placebo participants from concurrently enrolling regimens. Analyses of ALSFRS-R bulbar subdomain,

CNS-BFS, HHD, and SVC will use shared-baseline linear mixed models that adjust for time since onset of weakness, pre-baseline slope, baseline riluzole use, baseline edaravone use, baseline Nuedexta use, and site of onset and their interactions with time since baseline, and include random intercepts and slopes by regimen and by participant with unstructured covariance at each level. Given low expected event rates, time to bulbar onset and time to death or death equivalent will use log-rank tests. Per protocol analyses will also be performed to evaluate the effects of pridopidine on participants complying with study regimen. Details of endpoint measures, analysis samples, statistical models, and the closed-testing procedure will be described in the regimen-specific statistical analysis plan.

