2.0 (continued)	08 Aug 2022 (continued)	
case of time-dependent exclusions, and to specify that data from placebo participants from other regimens would not be excluded from the EPP analysis set due to non-adherence to protocol-specified dosing.
 
Revision of Section 6.2 Baseline Characterization to include ALSAQ-40 domain scores and SI and clarify reference to CNS-BFS total score and serum NfL level.
 
Revision of Section 6.3 Primary Efficacy Analysis and Supportive Analyses to include the ECM analysis set.
 
Revision of Section 6.5.1 Hierarchical Testing to correct reference to Section 6.5.6 for survival analyses.
 
Revision of Section 6.5.2 Repeated-measures Model to add a fixed term for treatment group (removing the shared-baseline assumption at the recommendation of the FDA) and to specify a separate supportive analysis that includes fixed terms for centered baseline serum NfL level and centered baseline serum NfL level \times visit interaction.
 
Revision of Section 6.5.3 Random-slopes Model to add a fixed term for treatment group (removing the shared-baseline assumption) and to specify a separate supportive analysis that includes fixed terms for centered baseline serum NfL level and centered baseline serum NfL level \times study month interaction.
 
Revision of Section 6.5.4 Time to First Evidence of Bulbar Dysfunction to reference the FAS and mITT analysis sets and to specify a separate supportive analysis that includes baseline serum NfL level as an additional covariate.
 
Revision of Section 6.5.5 Responder Analysis to specify a separate supportive analysis that includes baseline serum NfL level as an additional covariate.
 
Revision of Section 6.5.6 Survival and Time to Clinical Events to include the mITT and ECM analysis sets, to clarify that survival analyses that include follow-up beyond the placebo-controlled period will be analyzed in the ERO analysis set, to include baseline age as an additional covariate in adjusted models, and to specify an additional adjusted analysis that includes baseline serum NfL level as a covariate.
 
Revision of Section 6.5.7 CAFS to clarify that the primary CAFS analysis is specified in the ALS Master Protocol Recommended Statistical Analysis, Design and Simulation Report and to add two additional sets of CAFS analyses that adjust rank scores in

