- Time to first decline of 1 or more points post baseline in the ALSFRS-R bulbar domain (Q1-Q3) score among participants in FAS with bulbar dysfunction at baseline defined as an ALSFRS-R bulbar domain (Q1-Q3) score of less than 12,
- Proportion of participants experiencing no worsening in the ALSFRS-R bulbar domain (Q1-Q3) score from baseline through Week 24 among all participants in FAS with delta-FRS slower than -0.75 points/month (slow progressors),
- Proportion of participants with ALSFRS-R bulbar domain (Q1-Q3) score greater than or equal to 9 (out of 12) at Week 24 among all participants in FAS with bulbar dysfunction at baseline defined as an ALSFRS-R bulbar domain (Q1-Q3) score of less than 12,

- Proportion of participants experiencing no worsening in the ALSFRS-R bulbar domain (Q1-Q3) score from baseline through Week 24 among all participants in FAS with baseline ALSFRS-R greater than or equal to 36 (Early in disease),
- Rate of change in CNS-BFS total score from baseline through Week 24 among all participants in FAS,
- Rate of change in CNS-BFS total score from baseline through Week 24 among participants in FAS with bulbar dysfunction at baseline defined as an ALSFRS-R bulbar domain (Q1-Q3) score of less than 12,
- Change in HHD upper extremity percentage from baseline through Week 24,
- Change in HHD lower extremity percentage from baseline through Week 24,
- Change in log transformed serum NfL from baseline through Week 24 among all participants in FAS,
- Change in log transformed serum NfL from baseline through Week 24 among participants in FAS with bulbar dysfunction at baseline defined as an ALSFRS-R bulbar domain (Q1-Q3) score of less than 12,
- Change in log transformed serum NfL from baseline through Week 24 among participants in FAS by NfL median baseline split (slow vs fast progressors),
- Rate of change in ALSFRS-R total score from baseline through Week 24 among participants in FAS who were not on Nuedexta at baseline,
- Rate of change in ALSFRS-R total score from baseline through Week 24 among participants in FAS who were not on Nuedexta at baseline and with bulbar dysfunction at baseline defined as an ALSFRS-R bulbar domain (Q1-Q3) score of less than 12,
- Rate of change in CNS-BFS total score from baseline through Week 24 among participants in FAS who were not on Nuedexta at baseline,

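### The repeated-measures model in SAP 6.5.2 does not adjust for the endpoint's own baseline, so its Week 24 contrast is a change-score difference: valid, but usually less precise than it could be

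*SAP*

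**What the plan says.** SAP 6.5.2 states that the repeated-measures model and its main contrast "are revised from those specified in the M-SAP to include a main effect of treatment and main effects of centered baseline Nuedexta use", together with site of onset. The response in SAP 6.5.2 is the "value of the efficacy endpoint being tested for a given participant at a given visit", so the baseline visit enters as a row of the outcome. The fixed terms are visit, treatment, treatment by visit, and six covariates each with a visit interaction. The SAP defines z as follows: it "is the vector of covariates (centered time since onset, centered delta-FRS, centered baseline riluzole use, centered baseline edaravone use, centered baseline Nuedexta use", and site of symptom onset completes the list. The endpoint's own baseline is not in it. Within-participant covariance is unstructured.

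On the estimate the section states: "The primary estimate will be the treatment-dependent difference in change from baseline to the Week 24 Visit". The coded contrast is "trtrnd*visit 1 0 0 -1 -1 0 0 1 / cl", which is (Week 24 minus Week 0) on active less the same difference on placebo.

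Protocol 9.4 had a different form: analyses of the bulbar subdomain, CNS-BFS, "HHD, and SVC will use shared-baseline linear mixed models that adjust for time since onset of weakness" and other covariates. The SAP's version 2.0 entry explains that 6.5.2 was revised "to add a fixed term for treatment group (removing the shared-baseline assumption at the recommendation of the FDA". SAP section 1 gives the SAP precedence over the protocol on this matter.

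The endpoints at issue are worded as change, for example "Change in log transformed serum NfL from baseline through Week 24 among all participants in FAS" in SAP 4.1. They stand among the other secondary endpoints, outside the hierarchy. At its end, 6.5.2 plans a separate supportive analysis that adds baseline serum NfL and its interaction with visit.

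**The concern.** A shared-baseline model uses the correlation between baseline and Week 24 to sharpen the Week 24 comparison and to correct it for chance differences at baseline. Once each arm has a free baseline mean, that correction is lost, whatever the covariance structure. The usual way to recover it without assuming a common baseline mean is to use the baseline value as a covariate. The SAP dropped the constraint and did not add the covariate, so the baseline value, which is collected anyway, is used only by subtraction.

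At stake are precision and the handling of chance imbalance for the serum NfL secondaries (all participants, those with bulbar dysfunction, and by median split of baseline NfL) and for exploratory change endpoints such as home FVC, serum creatinine, ALSAQ-40 and CNS-LS. The two HHD secondaries may also be involved.

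**Working it through.** The plan states no sample size, SD, correlation or power for these endpoints, so there is no figure of its own to reproduce.

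**Inputs.** Model terms, code and contrast: SAP 6.5.2. Allocation: 120 active and 40 placebo (protocol summary). Shared placebo comes from regimens A, B and C (SAP 6.1), without a number; total placebo is assumed to lie between 40 and 160. The correlation rho between baseline and Week 24 and the SDs s0 and s24 are assumptions, all taken given the listed covariates.

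**1. What the contrast estimates.** Every visit has the same regressors, so with complete data generalised least squares gives the regression of (Week 24 minus baseline) on treatment and the covariates. The regimen random intercept is constant within a participant and cancels in the change. A numerical check with four visits agreed:

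| Setting | 6.5.2-type contrast | Change-score difference |
|---|---|---|
| 120 vs 40, no covariate | -0.13312 | -0.13312 |
| 120 vs 40, one covariate by visit | -0.13690 | -0.13690 |
| 120 vs 160, no covariate | -0.00662 | -0.00662 |

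The unstructured covariance therefore brings in no regression on baseline.

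**2. Precision.** Residual variance per participant:

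- as written: s0² + s24² - 2·rho·s0·s24
- own baseline as covariate: s24²·(1 - rho²)
- difference: (s0 - rho·s24)², which is never negative.

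With s0 = s24 = 1 these are 2(1 - rho) and 1 - rho², with ratio (1 + rho)/2. The excess CI width is 1/√ratio - 1. The last column takes an effect with 80% power as written: power = Φ(2.80/√ratio - 1.96).

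| rho | As written | Adjusted | Ratio | CI wider by | 80% power becomes |
|---|---|---|---|---|---|
| 0.5 | 1.00 | 0.75 | 0.75 | 15.5% | 90% |
| 0.7 | 0.60 | 0.51 | 0.85 | 8.5% | 86% |
| 0.8 | 0.40 | 0.36 | 0.90 | 5.4% | 84% |
| 0.9 | 0.20 | 0.19 | 0.95 | 2.6% | 82% |
| 0.95 | 0.10 | 0.0975 | 0.975 | 1.3% | 81% |

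Unequal SDs move this both ways. With s24/s0 = 1.25 and rho = 0.8, rho·s24 = s0 and the loss is nil. With s24/s0 = 0.8 and rho = 0.8, the ratio is 0.64 × 0.36 / (1 + 0.64 - 1.28) = 0.64. Under an assumed 20% monotone dropout and equal SDs, the shared-baseline form, whose complete-data ratio is also (1 + rho)/2, gave 0.778, 0.867, 0.912, 0.956 and 0.978 for the five correlations.

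**3. Chance imbalance.** Given a baseline difference d between arms, the planned estimate shifts by (rho·s24/s0 - 1)·d, which is (rho - 1)·d with equal SDs. In 4,000 simulated trials (120 vs 40, rho = 0.8) the shift was -0.21 per SD of imbalance (theory -0.20), against -0.01 with own-baseline adjustment. Both estimators averaged zero (0.0002 and -0.0002), and the variance ratio was 0.898 (theory 0.90). The standard error of d is √(1/120 + 1/40) = 0.18 SD, or √(1/120 + 1/160) = 0.12 SD. At rho = 0.8 an imbalance of one standard error thus shifts the estimate by 0.20 × 0.18 ≈ 0.04 SD or 0.20 × 0.12 ≈ 0.02 SD.

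**4. The supportive NfL analysis.** For the NfL endpoint, 6.5.2 would keep baseline NfL as an outcome row and also use it, by visit, as a covariate. The covariate then predicts the baseline row exactly, that residual variance is zero, and the unstructured matrix is singular.

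**The case against.** The planned analysis is valid and prespecified, and the constraint was removed on regulatory advice. The endpoints are non-hierarchical or exploratory and carry no power claim. If rho is 0.8 to 0.9 with equal SDs, the gain is only 2 to 4 power points from 80%. All of that stands and limits the weight of the point.

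For NfL, the section already plans an analysis with baseline NfL by visit. This also stands, but it is supportive only and cannot be fitted as coded (step 4). SAP 7.2 says analyses that do not converge will be omitted rather than reworked, so it could be lost. For other endpoints it adjusts for NfL, not for their own baseline.

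HHD may be outside the point. Its derivation is in the M-SAP, which was not available, and protocol 9.4 words it as percent change from baseline. If it is scaled to own baseline, the baseline is constant and there is nothing to adjust for. The imputation code in SAP 6.5.10 uses the baseline value as a predictor and names the HHD percentages, which hints the other way, but that code is a general template.

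The SAP does not name 6.5.2 as the main analysis of the change endpoints; the random-slopes model in 6.5.3 lists most of them too. The wording of the endpoints matches the estimand of 6.5.2, and 6.5.1 sends only rate-of-change endpoints to 6.5.3.

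**Conclusion.** The point holds as a cheap gain in precision, not as an error. The 6.5.2 contrast is a change-score difference adjusted for six covariates but not for own baseline. With equal SDs and rho from 0.5 to 0.9, the planned interval is about 15% to 3% wider than needed. These correlations are assumed, and the loss is nil when s0 = rho·s24.

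A reader might infer more than the documents support:

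- *That the estimate is biased.* It is unbiased over randomisations; the effect of imbalance is conditional on the baseline difference that happens to occur.
- *That precision is lost whenever rho is below 1.* That requires equal SDs.
- *That baseline imbalance is likely because most controls come from other regimens.* No count of shared placebo is given, and SAP 2.5 assigns participants to regimens at random.
- *That confirmatory results are at risk.* The primary analysis is a separate Bayesian model, and the only continuous endpoint in the hierarchy, SVC, is assigned to 6.5.3. The calculation here does not extend to that model.

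**What to change.** In SAP 6.5.2, for endpoints other than ALSFRS-R (and other than HHD if the M-SAP scales it to own baseline), model change from baseline at post-baseline visits only. Add the centered baseline value of the endpoint and its interaction with visit to the listed covariates, and take the treatment contrast at Week 24. Keep the current contrast as a sensitivity analysis. ALSFRS-R can stay as it is because delta-FRS is computed from the baseline total score, so its baseline is already partly represented.

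This does not bring back the shared-baseline assumption, and it still compares mean 24-week change between arms. Dropping the baseline row also removes the singularity in the supportive NfL analysis; for the NfL endpoint itself that analysis then coincides with the main one. State whether HHD is scored as percent of own baseline, and name the section that gives the main analysis of each change endpoint.

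The cost is SAP wording and one changed model statement. Participants with no post-baseline value leave the model; they carry almost no information on change. Those with a missing baseline need the mean imputation of SAP 3.6 or are left out, whereas the current likelihood model keeps them without imputation.
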